looked at its use during pregnancy). Prior to the recommendation to limiting the daily dose to 6 grams/day in humans, some physicians recommended up to 20 g/day, which approximates to 300 mg per kg/day⁷⁰.

Adverse Reactions^{13,24}: When dosed orally, nausea, diarrhea, bloating, headache, fatigue, insomnia, and difficulty concentrating have been reported. These adverse reactions however, do not appear to occur any more frequently in groups exposed to MSM than placebo in clinical trials¹³. There is no known drug-food, drug-drug, or drug-lab test interactions known²⁴.

Proposed use of MSM in Low Back Pain: As noted previously, MSM accounts for 4.1% of all nonvitamin, nonmineral CAM therapies used and is often cited as a remedy for back pain. Tant et al note that in a trial of glucosamine containing MSM, both yield symptomatic relief in patients with low back pain, individually and when taken together²⁵. Interestingly, trials such as that performed by Usha et al included MSM in the formulation of Glucosamine when assessing its impact on osteoarthritis¹⁴. However, additional information on the impact MSM may have on low back pain is lacking. Furthermore, of the 462 trials for low back pain registered with clinicaltrials.gov, none is designed to assess the impact of MSM on low back pain²⁶.

Patients continue to access information on CAM through a variety of sources. A lack of true clinical assessment of the usefulness of MSM in low back pain suggests that patients will continue to consume a product with a potential but unknown benefit. As a multidimensional approach to the treatment of low back pain is endorsed, the assessment of MSM on low back pain as an alternative or adjunctive therapy would be prudent. For this reason, we propose that a clinical trial be carried out to assess the impact of MSM on low back pain.

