Proposal of Materials and Methods: Selection of proper follow up time has been based on studies of MSM in osteoarthritis. Follow up time ranges from 2¹³ to 12 weeks¹². In the study by Kim et al¹³, efficacy was not noted until 4 weeks into the study. This improvement was even more notable at 8 and 12 weeks than at 4 suggesting that improvement in symptoms may require longer exposure MSM. For this reason, the impact MSM on low back pain, function and quality of life should be carried out to at least 12 weeks.

The use of 4 week intervals for reassessment mirrors the protocol by Kim et al. This is convenient considering the PIQ-6/R was designed for a 1 (acute) or 4 week (chronic) follow up.

Inclusion and Exclusion Criteria for this study will be similar to the common criteria from various studies on Low Back Pain^{42-44,52,55,58,61}.

Studies of MSM and osteoarthritis have recommended MSM dosing ranging from 500mg TID to 3 g BID^{12,13}. Doses of 6 g daily are considered safe^{13,24}. As noted above, studies in rats found that doses 5-7 times the maximum recommended daily amount may be given without any appreciable toxicity^{15,68}. Human studies using >6gm/day have not been performed. MSM will be given in the dose of 1500mg x2 Tabs, BID. Standard of care naproxen is typically defined as a dose of 225-550 mgs twice a day although it may vary depending on the provider.

3.5.1. Bibliography:

3. Teets RY, Dahmer S, Scott E. Integrative Medicine Approach to Chronic Pain.
5. Ernst E. Prevalence of use of complementary/alternative medicine: a systematic review. *Bull World Health Organ [online].* 2000; 78(2) 258-266

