 - Group 1 will take by mouth three 1000 mg capsules twice a day (6000 mgs) of MSM plus standard of care naproxen.
 - Group 2 will take by mouth three placebo capsules twice a day plus standard of care naproxen.
- Subjects will be asked to complete the following questionnaires:
 - RMDQ
 - PIQ-6
- Subjects will be asked “On a scale of 0-10, with 10 being the worst pain, what is your current level of pain”.
- Subjects will be asked if they are undergoing any other treatment for back pain, when the last treatment was, and whether or not they were satisfied.
- Subjects will be given a 12 week supply of the study pills and reminded to take the pills as instructed.
- Subjects will be given a Study Diary and will be instructed to record any missed dose of their study pills, record how much standard of care naproxen taken, and to bring the Study Diary to next visit.

Visit 2/Week 4:

- Record: Weight (in pounds), blood pressure, history of lower back surgeries, medical history, and concomitant medications.
- Subjects will be asked to complete the following questionnaires:
 - RMDQ
 - PIQ-6
- Subjects will be asked “On a scale of 0-10, with 10 being the worst pain, what is your current level of pain”.
- Research staff will record whether subject had any side effects to report.
- Subjects will have their study medications refilled.
- Research staff will collect the subject’s Study Diary, issue them a new one, and remind them to bring it with them to the next study visit.
- Research staff will remind subjects to take the pills as instructed.
- Subjects will have the following research-driven blood test drawn via 1 venipuncture (5-10 mls, approximately 1-2 teaspoons of blood drawn for each test) which include:
 - Comprehensive metabolic panel (liver function, renal function, plasma glucose tests).
**Subjects who have had a comprehensive metabolic panel test within the one week prior to this visit will not need to have this test repeated unless they are abnormal.*
 - Complete Blood Count.
**Subjects who have had a complete blood count test within the one week prior to this visit will not need to have this test repeated unless they are abnormal.*

Visit 3/Week 8:

- Record: Weight (in pounds), blood pressure, history of lower back surgeries, medical history, and concomitant medications.
- Subjects will be asked to complete the following questionnaires:
 - RMDQ
 - PIQ-6

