If a subject misses a dose, regardless of the amount, they will be encouraged to document this in their study diary and resume taking their pills. All subjects will remain in the study and continue with all the study related visits.

If a subject misplaces or loses their study medication, they will be instructed to return to the research department and will be given a new bottle of their assigned study medication. Since the research coordinator is not blinded, they will be able to give the medication that the subject was assigned.

If a subject forgets to bring their study medication in for their visit, they will be instructed to bring it in at their earliest convenience.

WITHDRAWAL PROCEDURES: If at any time during the study, the subject decides to withdraw consent or if the subject is withdrawn from the study by the investigator, they will be referred to their Primary Care Manager (PCM) to continue with standard of care treatment.

PREGNANCY: Subjects must agree to take precautions to prevent pregnancy during the course of this study due to the possible effect MSM may cause an unborn child. The only completely reliable methods of birth control are total abstinence or surgical removal of the uterus. Other methods, such as the use of condoms, a diaphragm or cervical cap, birth control pills, IUD, or sperm killing products are not totally effective in preventing pregnancy. In addition, women who are breastfeeding may not participate in this study.

If a subject unintentionally becomes pregnant, they will be instructed to cease taking their study pills, return their pill bottle and will be removed from the study.

DISPOSAL OF STUDY RELATED PILLS: Subjects will return any remaining study-related pills directly to the Research Coordinator or Principal Investigator. The Research Coordinator or Principal Investigator will be responsible for disposing of the study-related pills. The preferred method of disposal is to have the Pharmacy dispose of them. If the Pharmacy is unable to dispose of them, they will provide directions on safe disposal for the Research Coordinator or Principal Investigator to follow.

OTHER: Subjects will take their study pills daily and will be permitted to have the usual medical care for other co-morbid and acute conditions if applicable. Analysis described above using intention-to-treat principles for any missing data will be used (we will use the carry-forward method to impute missing data).

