 - History of high blood pressure.
 - History of heart, kidney, liver or ulcer disease.
 - Allergic to analgesics or Non-steroidal anti-inflammatory agents (NSAIDs).
 - Pregnant or breastfeeding.
 - Initial pain rating of greater than 8/10 on initial intake evaluation
 - If the comprehensive metabolic panel is reviewed by the PI, and any of the values are outside a range deemed safe for the subject to be included in study.
 - If any of these four components of the complete blood count is reviewed by the PI, and any of the values are outside a range deemed safe for the subject to be included in study:
 - White blood cell count
 - Hemoglobin
 - Hematocrit
 - Platelets

- Patients taking any of the following medications are excluded from participating, unless they agree to wash out for two weeks prior to entering the study:
 - Muscle relaxers of any type
 - Tramadol
 - Gabapentin
 - Pregabalin
 - Glucosamine
 - Narcotic pain medications
 - Non-steroidal anti-inflammatory agents (NSAIDs)

* Patients taking naproxen must agree to wash out for two weeks prior to entering the study, but can begin taking it again, as prescribed, after Visit 1 where a baseline pain assessment is performed.

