4.4. Assent Process: N/A

4.5. Benefits: The benefits to the subjects may include a decrease in lower back pain and increase in function.

4.6. Risks: Risks to the subject are minimal.

Since the interaction between MSM and the medications in the exclusion list that require a washout period (Muscle relaxers of any type, Non-steroidal anti-inflammatory agents (NSAIDs), Tramadol, Gabapentin, Pregabalin, Glucosamine, Narcotic pain medications) have not been studied, patients will be asked not to resume taking these medications while participating in this study.

Less likely and not serious:

- Risks related to Blood Draws:
 - Bleeding
 - Feeling light-headed
 - Bruising at the blood draw site
 - Infection
- Risks related to MSM:
 - Bloating
 - Constipation
 - Indigestion
 - Fatigue

- Decreased concentration
- Insomnia
- Headache

Rare and serious:

There may be a risk that the subject has an allergy to MSM that they are not aware of currently. The signs and symptoms of an allergic reaction include:

- Shortness of breath
- Hives (itchy rash)
- Runny nose
- Watery eyes
- Sore eyes
- Asthma
- Lip swelling
- Tongue swelling
- Nausea
- Bronchospasm (a bronchial spasm is a sudden constriction of the muscles in the walls of the bronchioles)
- Anaphylaxis (whole-body allergic reaction that has the following signs and symptoms):
 - Abdominal pain or cramping
 - Abnormal (high-pitched) breathing sounds
 - Anxiety
 - Confusion
 - Cough
 - Diarrhea
 - Difficulty breathing
 - Difficulty swallowing
 - Fainting, light-headedness, dizziness
 - Hives
 - Itchiness
 - Nasal congestion
 - Nausea, vomiting
 - Palpitations
 - Skin redness
 - Slurred speech
 - Wheezing

*If the subject experiences any of these symptoms, they are instructed to stop taking the study pills and seek urgent medical treatment.

There is also a potential risk of an inadvertent disclosure of personal health information.

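### The eligibility, washout and on-study medication rules never name the subject's own MSM, so the placebo arm can take the test product; the direction is towards no effect, the size is unknown

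*Combined protocol and SAP*

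**What the plan says.** The medication rule appears in full twice, in item 6 of the Protocol Summary and in section 3.6.7: "Patients taking any of the following medications are excluded from participating, unless they agree to wash out for two weeks" before entry. Both copies list muscle relaxers, tramadol, gabapentin, pregabalin, glucosamine, narcotics and NSAIDs. The opening paragraph of section 3.6 gives a shorter washout list without glucosamine, narcotics or MSM. No other inclusion or exclusion criterion mentions prior or current MSM use.

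For the study period, section 4.6 repeats the full washout list and says "patients will be asked not to resume taking these medications while participating in this study". The paragraph headed OTHER in section 3.6 adds that subjects "will be permitted to have the usual medical care for other co-morbid and acute conditions"; it is silent on own MSM.

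Some information is collected. Concomitant medications are taken at Screening, and Weeks 4 to 16 each record "history of lower back surgeries, medical history, and concomitant medications". The diary asks subjects to "record any missed dose of their study pills, record how much standard of care naproxen taken". At Visit 1 and Week 16, "Subjects will be asked if they are undergoing any other treatment for back pain"; Week 16 also asks about pain medication since the last visit. No rule acts on any of these answers, and section 6.3 has no analysis of them.

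The background in section 3.5 states that "MSM accounts for 4.1% of all nonvitamin, nonmineral CAM therapies used and is often cited as a remedy for back pain", and its pharmacology paragraph lists back pain among the conditions for which MSM continues to be used. Under Proposal of Materials and Methods it states "Human studies using >6gm/day have not been performed".

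**The concern.** The question in section 3.1 is MSM plus naproxen against placebo plus naproxen. It can be answered only if the placebo arm is free of MSM. The criteria screen out a neighbouring supplement but not the test product.

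Three routes are open:

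- A current MSM user can enrol, give a baseline that already contains any MSM benefit, and continue.
- A placebo subject can start MSM during the 12 weeks.
- Any subject can take MSM between Week 12, when study pills stop, and Week 16, which section 6.1 counts as one of the five repeated measures.

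If MSM is effective, a placebo subject taking it shrinks the difference between arms. A null result could then mean either that MSM does not work or that controls were taking it. Because MSM is never asked about by name, the two could not be separated with confidence afterwards.

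There is also an exposure question. Group 1 is assigned 6000 mg daily, so any own MSM takes a subject above the level that the background treats as the upper end of human study experience.

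**Working it through.** **1. Reproduce the plan's power (section 6.2).** Inputs given there: f = 0.4, total N = 68, 2 groups, m = 5 repetitions, correlation 0.8, β/α ratio 4.

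- Numerator df = (2 − 1)(5 − 1) = 4
- Denominator df = 68 − 2 − 4 + 1 = 63
- Noncentrality λ = f²·N·m / (1 + (m − 1)ρ) = 0.16 × 68 × 5 / 4.2 = 12.952
- Solving β = 4α with the noncentral F gives critical F = 2.5241, α = 0.04954, power = 0.80185

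These match the printed output (2.524097; 0.049538; 0.801850).

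**2. Dilute the contrast.** Let a share c of placebo subjects obtain the full MSM effect, with the standard deviation unchanged. The mean difference becomes (1 − c) of its true value, so f becomes f(1 − c) and λ becomes 12.952 × (1 − c)². The critical F stays at 2.5241.

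| Assumed c | λ | Power at 68 completers | Completers needed for the planned power (smallest even total) |
|---|---|---|---|
| 0% | 12.952 | 0.802 | 68 |
| 2% | 12.439 | 0.783 | 72 |
| 5% | 11.690 | 0.754 | 76 |
| 10% | 10.491 | 0.701 | 84 |
| 20% | 8.290 | 0.584 | 104 |

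The required number grows roughly as 1/(1 − c)², for example 68 × 1.562 ≈ 106 at 20%. The direct search gives 104 because the denominator df also rises. That exceeds the 100 subjects whom section 6.4 plans to enrol.

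**3. Sensitivity.** If users get only a fraction e of the effect, c is replaced by c·e. A 20% share at half effect is therefore the 10% row (0.701). As a simple two-group contrast with d = 2f = 0.8 and 34 per arm, power starts at 0.910 and falls to 0.880, 0.843 and 0.751 at 5%, 10% and 20%. The direction is the same; the level depends on the test.

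**4. Status of the inputs.** The values of c are assumptions, because no document gives a rate of own MSM use in this population. Full effect in every user is the worst case for those users. The table covers placebo-arm use only; it does not model a baseline already on MSM.

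**5. Exposure, by comparison of passages.** Section 3.6 assigns three 1000 mg capsules twice daily, that is 6000 mg. Any additional amount exceeds 6 g/day. Section 3.5 says in one place that human studies above that level do not exist, and in another that some physicians recommended up to 20 g/day before a 6 g limit was advised. No figure in the documents allows the effect of extra MSM in Group 1 to be computed.

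**The case against.** The omission cannot be disputed on the text, but its importance can.

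A reader might infer that MSM use is common among these patients, or that 4.1% is a contamination rate. Neither follows. The background says that MSM is often cited for back pain and continues to be used. The 4.1% is MSM's share of nonvitamin, nonmineral products, not the share of patients taking it. The statement that back pain is the leading reason for alternative medicine covers all such therapies, prayer and yoga included. Own use may be rare: at 2% the power loss is trivial, and 20% has no support in the documents.

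A reader might also add the osteoarthritis-study doses in section 3.5 to the trial dose and arrive at 7.5 to 12 g/day. The documents give no consumer dose, so they support only that the total would exceed 6 g. Extending the point to DMSO goes too far as well: section 3.5 mentions it as a dietary compound and an infused product, not as something subjects take for back pain.

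Partial safeguards exist. The glucosamine bar would catch glucosamine/MSM combinations, randomisation balances baseline users on average, and the recorded concomitant medications would allow some reporting by arm. The consent form and diary are not available here and might carry an instruction.

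All of this limits the size of the problem. None of it supplies a rule on MSM taken alone in the body of the protocol, and balance at baseline does not stop MSM use in the placebo arm.

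**Conclusion.** The gap is real and should be closed, but it is a correctable weakness of unknown and possibly small size, not a flaw that by itself invalidates the design. The two full medication lists, the section 3.6 summary and the section 4.6 restriction all leave the subject's own MSM unaddressed. If MSM is effective, own use in the placebo arm biases the comparison towards no effect. With assumed shares of 2% to 20% and full effect in users, power at 68 completers goes from 0.802 to between 0.783 and 0.584. Those figures illustrate the sensitivity and are not estimates. The planned sample size is correct on its own inputs; it simply presumes an undiluted contrast. On exposure, the finding is limited to this: the criteria permit totals above 6 g/day, and they must be reconciled with the background statements on amounts above that level.

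**What to change.** - Name non-study MSM, alone or in combination products, in both eligibility lists (Protocol Summary item 6 and section 3.6.7), in the section 3.6 washout summary and in the section 4.6 on-study restriction. Any washout length is for the sponsor to set and justify; the documents give no basis for carrying the existing two weeks over to MSM.
- Make clear whether the restriction runs to Week 16, since that visit is analysed.
- Ask about non-study MSM by name at Screening and at every visit.
- Add to section 6.3 that non-study MSM use will be tabulated by arm and visit and reported beside the main result.
- Reconcile the section 3.5 statements on amounts above 6 g/day with the eligibility rules.

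The cost is a short amendment, one question per visit and one table. The downside is that a few current MSM users are lost to recruitment or delayed.

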3.6.8. Instrumentation: N/A

4.0. Human Subject Protection:

4.1. Recruitment:

All potentially eligible patients will be offered an opportunity to participate. Primary Care Managers (PCMs) who are not part of the research team will be informed about the study and provided information on the inclusion/exclusion criteria. PCM referrals and posted advertisements will be utilized for recruiting subjects to the study. Some patients may be patients of the PI or AI, however, they will have the study staff recruit their patients to prevent any misconception of coercion or undue influence. If a potential subject is identified by the treating PCM and is interested in obtaining more information about the study, the patient will either be provided a contact number to the Research Staff, the Research Staff will be given the potential subject's contact information by the PCM with the patient's oral or written authorization, or the PCM will come and get the Research Staff to speak with the patient directly.

4.2. Consent Processes:

The PI, AI, or Research Coordinators will obtain Informed Consent on this study. Informed consent and HIPAA Authorization will be sought in advance from each prospective subject. Informed consent will be appropriately documented. [32 CFR 219.117] After discussion with one of the investigators, the subject will be given the opportunity to consent. The investigator will provide a written copy of the consent form and allow the subject to read it, review it with the subject, and answer questions. The subject may decline to consent, and no pressure will be applied. If the subject consents to be enrolled in the study, the proper signatures will be obtained, and a copy given to the subject.

4.3 Participation Compensation: Subjects will not be paid for participation in this study.

4.4. Assent Process: N/A

4.5. Benefits: The benefits to the subjects may include a decrease in lower back pain and increase in function.

4.6. Risks: Risks to the subject are minimal.

Since the interaction between MSM and the medications in the exclusion list that require a washout period (Muscle relaxers of any type, Non-steroidal anti-inflammatory agents (NSAIDs), Tramadol, Gabapentin, Pregabalin, Glucosamine, Narcotic pain medications) have not been studied, patients will be asked not to resume taking these medications while participating in this study.

Less likely and not serious:

- Risks related to Blood Draws:
 - Bleeding
 - Feeling light-headed
 - Bruising at the blood draw site
 - Infection
- Risks related to MSM:
 - Bloating
 - Constipation
 - Indigestion
 - Fatigue

- Decreased concentration
- Insomnia
- Headache

Rare and serious:

There may be a risk that the subject has an allergy to MSM that they are not aware of currently. The signs and symptoms of an allergic reaction include:

- Shortness of breath
- Hives (itchy rash)
- Runny nose
- Watery eyes
- Sore eyes
- Asthma
- Lip swelling
- Tongue swelling
- Nausea
- Bronchospasm (a bronchial spasm is a sudden constriction of the muscles in the walls of the bronchioles)
- Anaphylaxis (whole-body allergic reaction that has the following signs and symptoms):
 - Abdominal pain or cramping
 - Abnormal (high-pitched) breathing sounds
 - Anxiety
 - Confusion
 - Cough
 - Diarrhea
 - Difficulty breathing
 - Difficulty swallowing
 - Fainting, light-headedness, dizziness
 - Hives
 - Itchiness
 - Nasal congestion
 - Nausea, vomiting
 - Palpitations
 - Skin redness
 - Slurred speech
 - Wheezing

*If the subject experiences any of these symptoms, they are instructed to stop taking the study pills and seek urgent medical treatment.

There is also a potential risk of an inadvertent disclosure of personal health information.

